## Statistical Analysis

The primary analysis will be conducted following the intention-to-treat principle. All tests will be two-sided with alpha set at 0.05. No adjustment will be made for multiple testing for multiple outcomes.

Baseline characteristics and outcomes will be summarized using appropriate descriptive statistics: mean (standard deviation) or median (P25~P75) for continuous variables, counts (%) for categorical variables. For continuous variables, Analysis of Variance (ANOVA) or Kruskal-Wallis test will be used to examine the differences among the three intervention groups and the control group as appropriate. For categorical variables,  $\chi^2$  or Fisher exact test will be carried out as appropriate.

Given an anticipated low rate of loss-to-follow up concerning the primary outcomes, the primary analyses will be conducted following a complete case strategy. Specifically, the neonatal hemoglobin and the change in maternal hemoglobin will be analyzed using mixed linear regression model (with necessary transformation for better normality) or mixed median regression model, where study center will be modelled as

a random effect. Potential confounding factors that differ among groups at baseline will be adjusted. Non-inferiority test will be employed with respect to the effect of delayed cord clamping on the change in maternal hemoglobin, in which the margin of non-inferiority is set at 0.87 g/dL, an expected clinically significant difference of the change in maternal hemoglobin. Non-inferiority would be concluded if the lower limit of the confidence interval was greater than -0.87 g/dL. If significant differences are observed in neonatal hemoglobin between groups, appropriate methods (such as trend test) will be used to further explore the association between different time of umbilical cord clamping and neonatal hemoglobin level. Center-stratified analysis will be carried out with generalized linear regression model to determine whether the effect on primary outcomes varies across centers.

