Secondary analyses will also be conducted only among complete cases. Mixed linear regression model (with necessary transformation for better normality) or mixed median regression model will be used to evaluate the effects of delayed cord clamping on the Apgar score, placental weight, maternal hemoglobin after the cesarean, and estimated maternal blood loss. Mixed logistic regression model will be fitted to assess the effects on the incidence rate of neonatal anemia, neonatal jaundice, neonatal intensive care unit (NICU) admission, and maternal blood transfusion. Center effects will be modeled by including a random effect. Potential confounding factors that differ among groups at baseline will be adjusted.

Multiple imputation method will be applied to deal with missing values before the analysis of exploratory secondary outcomes, if needed, and the results based on imputed data will be compared with those based on complete cases. Mixed linear regression model (with necessary transformation for better normality), mixed median regression model and mixed logistic regression model will be constructed as appropriate to estimate the effect on follow-up outcomes of children. These outcomes primarily include the hemoglobin and anemia at 6, 12, 18 months, the Z-score of length and weight at 3, 6, 12, 18 months, and the results of Denver Developmental Screening Test (DDST) at 3, 6, 12, 18 months. Random effects of centers and months of follow up will be set in models for the dependencies among observations nested within individuals and centers. Length and weight at birth are the pre-specified covariates for the models of follow-up length and weight, respectively. Baby sex is the pre-specified covariate for the model of the DDST result. Other confounding factors that differ among groups at baseline will be adjusted.

Sensitivity analysis will be performed on the basis of per-protocol dataset to confirm the robustness of the main result of two primary outcomes. Participants will be considered as compliant with the protocol if the time of cord clamping is as follows:

Arms	Anticipated procedure	Permissible time range
Control group	Immediately clamp	< 15s
Experimental group1	Clamp at 30s after delivery	≥15s and < 45s
Experimental group2	Clamp at 60s after delivery	≥45s and < 75s
Experimental group3	Clamp at 90s after delivery	≥75s and < 105s

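### The only effect model for follow-up weight adjusts for birth weight, very probably recorded after the randomised clamping, so its arm coefficient need not be the total effect of clamping on later weight

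*SAP*

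**What the plan says.** In the SAP's Statistical Analysis section, the paragraph on the exploratory secondary outcomes plans mixed models that "will be constructed as appropriate to estimate the effect on follow-up outcomes of children". The outcomes include "the Z-score of length and weight at 3, 6, 12, 18 months". For these models, "Length and weight at birth are the pre-specified covariates for the models of follow-up length and weight, respectively". After naming sex as the covariate for the developmental test, the paragraph adds: "Other confounding factors that differ among groups at baseline will be adjusted".

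The per-protocol table at the end of the section defines the arms by clamping time, from immediate clamping to "Clamp at 90s after delivery", with a permitted range in the last arm of up to just under 105 s.

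Three other planned analyses bear on the point:

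- Earlier in the section, "Baseline characteristics and outcomes will be summarized using appropriate descriptive statistics", and measurements on a continuous scale are then compared across arms: "Analysis of Variance (ANOVA) or Kruskal-Wallis test will be used to examine the differences among the three intervention groups and the control group".
- Where multiple imputation is used, "the results based on imputed data will be compared with those based on complete cases".
- The per-protocol sensitivity analysis covers the two primary outcomes only.

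**The concern.** Adjusting for a variable fixed before randomised treatment leaves the target of a linear treatment comparison unchanged and usually sharpens it. Adjusting for a variable that treatment may have altered can change the target. Birth weight looks like a baseline variable, and the SAP's wording about other baseline confounders appears to place it there. In this trial, however, the intervention happens in the first seconds after delivery, before a newborn would normally be weighed.

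If later clamping alters recorded birth weight, for instance through blood passing from the placenta, the model compares children with equal weights after clamping. Part of any effect of clamping on weight is then held constant. The coefficient answers a legitimate question, but not necessarily the one that a reader will take from a model described as estimating the effect on follow-up outcomes. For a gain in birth weight, the difference counts against the later-clamped arms.

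**Working it through.** The SAP states no figure on this point, so there is none to reproduce. The check has four steps.

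**1. Order of events.** From the SAP: clamping is at 0 to 90 s after delivery, with under 105 s permitted in the last arm. The SAP does not give the weighing time. That weighing follows clamping is an inference, though a strong one.

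**2. Could clamping change birth weight?** The SAP does not say so. It does make neonatal hemoglobin a primary outcome and placental weight a secondary one, so it treats blood transfer across the cord as something that clamping time may change. That makes a shift plausible but does not establish one.

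**3. Does another planned analysis give a modelled effect without birth weight?**

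- The ANOVA or Kruskal-Wallis comparison may cover follow-up weight and birth weight, but it names no variables, is an overall four-arm test, and models neither centre nor repeated visits.
- The comparison of imputed with complete-case results varies the handling of missing data, not the covariates.
- The per-protocol analysis does not reach follow-up weight.

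**4. Size.** Let T be the total effect on later weight Z, d the shift in birth weight caused by clamping, SD the standard deviation of birth weight, and b the slope of later Z on birth weight in SD units. Suppose mean Z = a + c·arm + b·(birth weight / SD), without interaction. Averaging within arms gives T = c + b·d/SD, so the adjusted coefficient is

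c = T − b·d/SD.

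The gap −b·d/SD does not depend on T and does not shrink with sample size. All inputs below are assumptions. For the standard errors I also assume outcome SD 1, within-child correlation 0.7, 200 children per arm, and one slope for all four visits. The variance of the four-visit mean is V = (1 + 3 × 0.7)/4 = 0.775, and the adjusted SE is sqrt((V − b²) × 2/200).

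| Shift d | SD | b | Gap (Z) | Adjusted SE | Gap in SEs |
|---|---|---|---|---|---|
| 0 g | any | 0.4 | 0 | 0.078 | 0 |
| 30 g | 450 g | 0.3 | −0.3 × 30/450 = −0.020 | sqrt(0.685 × 0.01) = 0.083 | 0.24 |
| 50 g | 425 g | 0.4 | −0.4 × 50/425 = −0.047 | sqrt(0.615 × 0.01) = 0.078 | 0.60 |
| 100 g | 400 g | 0.5 | −0.5 × 100/400 = −0.125 | sqrt(0.525 × 0.01) = 0.072 | 1.73 |

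A two-arm simulation with 400,000 children, true total effect 0, b = 0.4 and SD 450 g agrees with the formula. The adjusted coefficient was −0.043 at 50 g (formula −0.4 × 50/450 = −0.044) and −0.092 at 100 g (formula −0.089). Without birth weight it was 0.001 and −0.005.

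**Precision.** The unadjusted SE at 200 per arm is sqrt(0.775 × 0.01) = 0.088. Root mean squared error as an estimate of T, adjusted against unadjusted:

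- 0 g: 0.078 against 0.088
- 30 g: sqrt(0.020² + 0.00685) = 0.085 against 0.088
- 50 g: sqrt(0.047² + 0.00615) = 0.091 against 0.088
- 100 g: sqrt(0.125² + 0.00525) = 0.144 against 0.088

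The two models break even when b²(d/SD)² = b² × 2/n, that is, at d = SD × sqrt(2/n). For SD 400 to 450 g this is 57 to 64 g at 100 per arm, 40 to 45 g at 200, and 18 to 20 g at 1000.

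**The case against.** The strongest reply is that the SAP's Objectives name children's growth. Later size given starting size is a coherent meaning of growth, and adjusting for birth size is a direct way to study it. The SAP nowhere says that it wants the total effect on attained weight, and it names the covariate openly. Crude arm summaries of outcomes are already planned, and in a randomised trial these let a reader see the unconditional contrast. Every input to the size calculation is assumed, including a single slope from 3 to 18 months; a slope of 0.25 instead of 0.4 would cut the 50 g gap to 0.25 × 50/425 = 0.029 Z. For small shifts the SAP's model estimates even the total effect with lower mean squared error.

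Much of this stands. The adjusted model answers a fair question and should stay. The gap may be small or zero, and the document cannot show otherwise.

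Two things remain. First, the SAP describes these models as estimating an effect on follow-up outcomes, which is naturally read as the total effect, and it does not say which result answers that question if the crude and adjusted comparisons disagree. Second, the advantage in mean squared error depends on a shift that is unknown when the plan is written. The model without birth weight targets the total effect whether or not there is a shift.

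**Conclusion.** The concern holds in a limited form. The only modelled effect on follow-up weight is conditional on a variable very probably recorded after the randomised intervention and possibly changed by it. Its distance from the total effect is slope × shift / SD. Under the assumed cases this runs from 0 to 0.125 Z, and the true value is unknown and may be small. It is minor: one exploratory outcome is involved, and the primary outcomes are untouched.

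A reader might infer more than the SAP supports:

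- **That the follow-up weight estimate is biased.** This needs a shift in birth weight, which the SAP does not establish.
- **That the adjusted model is wrong and should go.** It is a legitimate analysis of growth at equal birth weight, and for small shifts it is the more precise one.
- **That birth length is clearly safe, or clearly affected.** The SAP puts length and weight in one sentence and gives nothing that settles the matter for length.

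**What to change.** Add a few sentences to the paragraph on exploratory outcomes:

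- Fit the same mixed model for follow-up weight Z-score also without birth weight, keeping the planned centre and follow-up random effects and using only covariates fixed before clamping.
- Base any statement about the total effect of clamping on follow-up weight on that model.
- Report the birth-weight-adjusted model beside it, labelled as later weight (growth) at equal birth weight.
- Show birth weight by arm, which the planned descriptive tables may already do.

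No new data are needed. The cost is precision in the added model. At a single visit its intervals are wider by 1/sqrt(1 − r²), where r is the correlation of birth weight with later weight Z: 1.048 at r = 0.3 and 1.155 at r = 0.5 (both assumed), or about 5 to 15%. If the true shift is below the break-even, the added model also has the higher mean squared error, which is a further reason to keep both.

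### Non-inferiority on maternal hemoglobin is decided on the intention-to-treat analysis alone; the planned per-protocol analysis has no role in the decision, so dilution from off-target clamping could favour the claim

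*SAP*

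**What the plan says.** All of this stands in the SAP, section Statistical Analysis.

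- Primary set: "The primary analysis will be conducted following the intention-to-treat principle". For the primary outcomes, "the primary analyses will be conducted following a complete case strategy".
- Level: "All tests will be two-sided with alpha set at 0.05". The confidence level of the non-inferiority interval is not stated separately.
- Decision rule for the change in maternal hemoglobin: "Non-inferiority would be concluded if the lower limit of the confidence interval was greater than -0.87 g/dL". The rule names no analysis set, so it falls to the primary one.
- Per-protocol set: "Sensitivity analysis will be performed on the basis of per-protocol dataset to confirm the robustness of the main result of two primary outcomes". Compliance is judged on actual clamping time: under 15 s for control, then 15 to under 45 s, 45 to under 75 s, and 75 to under 105 s for the three delayed arms.

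The SAP does not say whether non-inferiority must hold in both sets, or how a disagreement is to be read. It gives no expected rate or direction of off-target clamping.

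**The concern.** The same hierarchy serves two different questions. Neonatal hemoglobin is tested for a difference, and there a diluted contrast works against the claim. The change in maternal hemoglobin is tested for non-inferiority, and there a diluted contrast works in favour of the claim. A rule that is cautious for the first outcome need not be cautious for the second.

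The arms differ by tens of seconds and their compliance windows adjoin. If delay adds to maternal loss, two kinds of deviation bring a delayed arm closer to control: late clamping in the control arm, and early clamping in the delayed arm. Under the SAP's windows a control can be non-compliant only by being clamped late.

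At stake is the maternal safety conclusion. As the rule is written, non-inferiority could be claimed from the intention-to-treat interval while the per-protocol interval crosses the margin.

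**Working it through.** **Inputs from the SAP.** Margin 0.87 g/dL; two-sided alpha 0.05; intention-to-treat primary; clamping windows as above. The SAP shows no sample size, SD or power, so there is no figure of its own to reproduce.

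**Assumed inputs.** The interval is two-sided 95%, so the nominal error per comparison is 1 - Φ(1.96) = 2.5%. The standard error (SE) of the difference is 0.10 to 0.20 g/dL; for example, SD 1.0 with 200 or 50 women per arm gives 1.0 × √(2/200) = 0.10 or 1.0 × √(2/50) = 0.20. The net attenuation f is the fraction by which off-target clamping shrinks the difference.

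**Formula.** Let the difference under clamping as assigned be exactly -0.87. The intention-to-treat difference is then -0.87 × (1 - f), and

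P(lower limit > -0.87) = Φ(0.87 × f / SE - 1.96).

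| f | SE 0.10 | SE 0.15 | SE 0.20 |
|---|---|---|---|
| 0 | 2.5% | 2.5% | 2.5% |
| 5% | Φ(0.435 - 1.96) = 6.4% | Φ(0.290 - 1.96) = 4.7% | Φ(0.2175 - 1.96) = 4.1% |
| 10% | Φ(0.870 - 1.96) = 13.8% | Φ(0.580 - 1.96) = 8.4% | Φ(0.435 - 1.96) = 6.4% |

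**What f means in clamping times.** If the effect is linear in time, 10% of the 90 s arm clamped at 60 s gives f = 0.10 × 30/90 = 3.3%, and an error of 3.5% (SE 0.20) to 4.7% (SE 0.10). If 10% of controls are clamped at 30 s, f is 0.10 × 30/30 = 10% for the 30 s arm, 5% for the 60 s arm and 3.3% for the 90 s arm. The arm with the shortest delay is the most exposed.

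**Direction.** A simulation used a linear effect reaching -0.87 at each arm's target time, 100 women per arm, SD 1.5 g/dL, a timing SD of 10 s in the delayed arm and 15,000 runs. The error rates for the 30/60/90 s arms, each set taken alone, were:

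| Timing pattern | Intention-to-treat | Per-protocol |
|---|---|---|
| Symmetric errors | 2.6 / 2.6 / 2.5% | 2.5 / 2.6 / 2.4% |
| 10% of controls clamped at 30 s | 5.8 / 4.0 / 3.3% | 2.4 / 2.5 / 2.5% |
| Delayed arm 10 s early on average | 27.3 / 10.5 / 6.6% | 9.7 / 5.7 / 4.0% |
| Delayed arm 10 s late on average | 0.03 / 0.5 / 1.0% | 0.4 / 1.3 / 1.6% |

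The error rises only when the arms move closer together. In both patterns where that happens, the per-protocol analysis has the lower error. A rule that requires both sets cannot have a higher error than the smaller of the two columns. It does not always reach 2.5%, because a systematic shift of 10 s leaves many women inside their window, and the per-protocol set keeps them.

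**The case against.** The strongest reply has four parts.

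1. *Inflation is not established.* A reader might infer that the false-claim rate does exceed 2.5%, because the SAP defines permissible windows and so must expect deviations. That does not follow: any per-protocol set needs a definition of compliance, and defining one predicts neither the frequency nor the direction of deviations. A reader might also suppose that every clamping in a neighbouring window dilutes the contrast. It does not: a woman assigned 30 s and clamped in the 60 s window moves away from control. This part of the reply stands, and the point is therefore conditional.

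2. *Intention-to-treat answers its own question.* For the effect of assigning a clamping time, the test keeps its nominal level. This stands. The inflation is against the effect of clamping carried out as assigned, and the SAP does not say which of the two effects the maternal claim concerns.

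3. *The per-protocol analysis is already planned for this outcome, so a disagreement would be visible.* This is true, and it narrows the gap. But visibility is not a rule: nothing says that a failed confirmation changes the conclusion.

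4. *The per-protocol set is no safe harbour.* It is selected on actual clamping time, a post-randomisation variable, and can itself be biased. This stands as a reason to require both sets, not as a reason to rely on either one alone.

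**Conclusion.** The point holds in conditional form. The SAP lets non-inferiority on the change in maternal hemoglobin rest on the intention-to-treat complete-case analysis alone, and gives the per-protocol analysis no say. Where off-target clamping draws the arms together on net, the chance of declaring non-inferiority at a true difference of -0.87 g/dL under clamping as assigned rises above nominal: to about 4-6% with 5% attenuation and about 6-14% with 10%.

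These figures rest on an assumed two-sided 95% interval and an assumed SE of 0.10 to 0.20 g/dL. Larger figures can be produced by supposing that many women revert fully to immediate clamping, but nothing in the SAP supports that. Nor does the SAP show that any inflation will occur. What it does show is a decision rule unprotected against it, in a plan that already contains the analysis needed for partial protection.

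**What to change.** Amend the decision rule in the SAP, section Statistical Analysis, to state:

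- Non-inferiority for a delayed arm is concluded only if the lower limit of the two-sided 95% confidence interval exceeds -0.87 g/dL in both the intention-to-treat and the per-protocol sets.
- If the two sets disagree, the result is reported as non-inferiority not shown.
- The distribution of actual clamping times is reported by arm, so that a reader can judge the direction and size of any dilution.

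Leave intention-to-treat alone as decisive for neonatal hemoglobin.

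The cost is a few sentences, since the per-protocol analysis of this outcome is already planned. There is some loss of power, because two intervals must clear the margin and the per-protocol set is smaller. The per-protocol set also remains selected on a post-randomisation variable, so the amended rule reduces the inflation without guaranteeing 2.5%.
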